Intensive home blood pressure lowering in advanced chronic kidney disease: a pilot randomized controlled trial

Study Protocol

NCT02975505

Document date: February 13, 2025

Study design

This pilot study is a non-blinded randomized controlled trial investigating the safety and feasibility of strict blood pressure control in patients with advanced CKD. Patients will be randomized in 2:1 ratio to intervention (home SBP target < 120 mmHg) or usual care (home SBP target 130-140 mmHg) until 75 patients are enrolled, and then subsequently patients will be randomized in 1:1 ratio to intervention or usual care. Antihypertensive medications will be titrated as needed to achieve target home SBPs over the course of 4 months and maintained thereafter until study closeout (see Figure 1). Biannual visits are conducted after month 12.

Study population

All patients are recruited from the University of California San Francisco nephrology clinics. Inclusion and exclusion criteria are as follows:

Inclusion criteria:

- 1. ≥ 18 years of age
- 2. English-speaking
- 3. Patients with advanced CKD who meet the eGFR criteria defined as either
 - a. at least two eGFRs ≤30 mL/min/1.73m² in the last three months
 - b. a prior diagnosis of CKD and at least one eGFR ≤30 mL/min/1.73m² in the last three months.
- 4. Presence of elevated BP, defined as receipt of one or more antihypertensive agents or an office SBP>140 mmHg at the time of the screening visit. If the participant is not on antihypertensive medications, they must have an average home SBP>130 mmHg during the first week of the study when baseline home BPs are ascertained.
- Participants must have a mid-arm circumference between 22-37 cm and access to a smart phone or tablet in order to use the Bluetooth-enabled home BP device, QardioArm[®].

Exclusion criteria:

Patients are excluded if they:

- 1. are planning to become pregnant or are currently pregnant
- 2. are marginally housed due to concerns regarding follow-up
- 3. are institutionalized or a prisoner
- 4. are actively participating in a different interventional trial that may affect blood pressure
- 5. are actively abusing illicit drugs and alcohol
- 6. have a history of poor compliance
- 7. take >5 antihypertensive medications (including diuretics) at maximum doses
- have cognitive impairment and are unable to follow instructions regarding home BP measurement during screening visit

If patients meet all inclusions and exclusion criteria, we will check with their nephrology providers prior to approaching participants to ensure their candidacy in our study.

Baseline Visit

During the baseline visit, participant eligibility is confirmed, written consent is obtained, and demographic, co-morbidity, and laboratory data are collected. A brief physical examination is performed and three automated office BP readings in the seated position followed by two standing BP readings are recorded one minute apart after five minutes of quiet rest. At the baseline visit, enrollees are provided with a QardioArm® device and trained to use the device to take standardized home BP measurements.

Participants are asked to take home BPs for a one-week baseline period to ensure continued eligibility and compliance with our protocol prior to randomization, with a minimum of 6 readings required over the one-week period. Participants are also asked to complete 24-hour ambulatory blood pressure monitoring (ABPM) during their baseline period. Patients who refuse to undergo 24-hour ABPM are not excluded from study.

Randomization

Eligible patients who complete the one week of baseline home readings will be randomized to either a home SBP target of <120 mmHg (intervention group) or 130-140 mmHg (usual care group) in 2:1 ratio until 75 participants are enrolled, and participants will be subsequently randomized in 1:1 ratio thereafter. The rationale for the 2:1 ratio for the first 75 patients is to ensure that we initially capture enough safety data on participants randomized to intervention, but we plan to transition to 1:1 ratio randomization thereafter. We will conduct a sensitivity analysis comparing the effect during the 2:1 randomization phase of the trial and 1:1 phase to determine if there is an interaction between the intervention and the phase of the trial.

Once patients are screened and deemed eligible, study personnel will notify nephrologists of their patients' eligibility and obtain assent for patient participation in the trial prior to randomization. Stratified permuted-block randomization will be performed with stratification by diabetes status in order to ensure that patients with diabetes who have previously been excluded from many trials of intensive BP lowering (8–10) are represented in our pilot study. Investigators will be blinded to the ordering of the randomization blocks and their respective sizes. The generation of allocation sequence is performed by and only accessible to the study coordinator for assignment of participants to the intervention and not accessible to investigators. Patients are contacted via phone or secure messaging to begin active titration of their antihypertensive regimens to achieve their assigned target SBPs after randomization.

Home blood pressure monitor

QardioArm[®] is a wireless Bluetooth-enabled home BP monitor that is validated by the European Society of Hypertension Protocol and the American Heart Association (31) and has a strong direct linear correlation (r=.96) with the previously validated and widely accepted Omron M3[®] BP device (32). The device is compatible with most smartphones and allows for real-time

wireless transmission of BP readings through an online phone application. The device is also accompanied by a secure platform used by providers for BP data transmission, monitoring, download, and storage. All participants are provided a device at no cost, and Bluetooth linkage between the device and smartphone are setup by study personnel at the baseline visit.

Office BP readings during study visits

Office BPs are measured at the baseline, 2, 4, 8, and 12-month study visits (Figure 1), and every six months thereafter. Participants are seated quietly in a room with the study coordinator for 5 minutes before BPs are taken. Three measurements are taken one minute apart. Participants are then be asked to stand for two minutes and two standing BPs are recorded one minute apart. One study coordinator will be present during all office BP measurements.

Intervention

Blood Pressure Targets

We have chosen to target home SBP, as opposed to mean arterial pressure (MAP) or diastolic BP (DBP) based primarily on the CV and mortality benefits seen recently in SPRINT (8) and data that suggest that SBP is a stronger predictor of ESKD risk and CV disease than DBP or MAP (24,33,34). Our usual care group will be treated to home SBP targets of 130-140 mmHg (equivalent to office SBP of 135-145 mmHg) because this was the range of BPs that screened patients had at baseline enrollment under routine care. During routine clinical care, any non-study provider can titrate antihypertensive agents as per their preference outside of the study protocol based on the clinic BP readings and other data available to them, and such titrations are noted and will be accepted by the study team. Home BP readings are made readily available to non-study providers upon request, and all nephrology clinic providers are alerted of patient enrollment in the study and the assigned BP target following randomization.

Home blood pressure readings

Participants are asked to measure their BPs at home on any three days of the week. For each day, participants take 3 readings in the morning and 3 in the evening. Participants are instructed to rest for 5 minutes before taking readings and sit quietly for 1 minute in between readings. Weekly home BP averages are calculated from the most recent 18 readings in a given week. Antihypertensive medications will be titrated by study investigators based on the average of the most recent 18 home BP measurements received, with a minimum of 6 required readings per week to be considered sufficient for any changes to medications. An insufficient number of measurements will prompt contact with the participant to increase the number of readings.

Antihypertensive Therapy Titration Intervention

Antihypertensive medications are titrated during the first 4 months to achieve target home SBP levels in both the intervention and usual care groups if home BP readings are not already within the target range. The antihypertensive therapy titration intervention will be individualized according to each patient's medical history, current medication regimen, and medication preference as specified by their nephrologist. Participants' referring nephrologist will be informed of their participation at the time of enrollment and asked to indicate which BP agents they would prefer to withdraw or add if SBP is outside of target according to their own practice patterns. Doses of current antihypertensive agents may be preferentially increased or decreased first depending on patient's home BP readings relative to their target SBP. This will be the first-line approach to avoid introduction of multiple new medications if doses of current medications are not yet optimized. New agents may be prescribed or discontinued after careful consideration of patient's medical history and nephrologist's input. Combination drugs will be acceptable but only used if suggested by the participant's nephrologist, as there may be cost barriers to the use of combination drugs. Although every antihypertensive treatment regimen will

likely differ for each participant, the suggested order of antihypertensive agent titration (if the nephrologist does not indicate a specific preference) will be angiotensin receptor blockers (ARBs) or angiotensin-converting enzyme inhibitors (ACEi) as first-line therapy, followed by (in order of preference) diuretics, calcium-channel blockers, beta-blockers, vasodilators/nitrates, sympatholytics, alpha-blockers, and potassium-sparing diuretics. See Figure 2 for the antihypertensive medication titration protocol.

We will permit up to a 30% increase in serum creatinine level after ACEi/ARB initiation or uptitration of dosages of other antihypertensive medications, in accordance with traditional guidelines and published literature (35,36). For patients who experience >30% increase in serum creatinine, the ACEi/ARB dose or other antihypertensive medication will be reduced, with plans for a repeat serum creatinine within 2 weeks. If the serum creatinine continues to be elevated, then the ACEi/ARB will be discontinued. We will also respect the opinion of the patient's nephrologist on this issue. If a nephrologist is concerned about any rise in serum creatinine, we will reduce or discontinue the drug. We will then proceed with the next suggested class of antihypertensive agents to help achieve the target blood pressure.

During the first 8 months of the study, participants will be contacted every other week by study coordinators to note any adverse events including dizziness, falls, syncope, hospitalizations, emergency room visits, acute kidney injury, CV events, or allergic reactions, as well as adherence to medication regimen and medication side effects such as diuresis, impotence, cough, lack of energy and sleepiness, lightheadedness on standing, or headaches.

Laboratory Tests

Basic metabolic panel and urine chemistry laboratory tests are obtained at baseline and at months 1, 2, 4, 8, 12, and every six months thereafter but timed as closely to clinical laboratory tests as possible (to avoid additional burden on participants) in a pragmatic approach. Labs are closely monitored by study investigators and medications titrated

accordingly to ensure the safety of all participants. Additional laboratory testing is performed as needed.

Follow-Up Timeline

The timeline of study visits during the one-year of follow-up is outlined in Figure 1. Participants are instructed to take weekly home BP readings for the first 4 months of the study, or until target SBP levels are achieved for two consecutive weeks. Once participants reach target SBP levels, home BP readings can be taken on a monthly basis over a one-week period each month. If participants maintain their target SBP levels after 8 months, home BP readings can be taken every two months thereafter. Participants will maintain their respective SBP target levels for the remainder of the study after month 8. If mean weekly SBP readings are > 4 mmHg outside the target range, antihypertensive therapy titration is resumed weekly until target SBP levels are achieved again for two consecutive weeks.

Participants are seen in person at Months 2, 4, 8, and 12, and every 6 months thereafter, but visits will be timed as close to their clinical visits as possible to avoid additional burden on participants in a pragmatic approach. In-person follow-up visits consist of a brief physical exam, office BP readings which will be obtained and used to calibrate the QardioArm® device to ensure accuracy of its readings, and laboratory testing. Patients will be contacted throughout the study via phone or secure text messages depending on patient preference. Adherence to antihypertensive therapy treatment will be assessed by administering a questionnaire during every in-person visit and follow-up phone call to ask participants if they are taking antihypertensive medications as prescribed and if they missed any doses since last follow-up. Adverse events (including emergency room visits or hospitalizations) and onset of ESKD, defined as initiation of chronic dialysis or receipt of kidney transplant, are also ascertained during follow-up. Participants will be followed indefinitely unless they choose to disenroll from the study or are lost to follow-up.

Outcomes measures

The primary outcome will be feasibility of achieving at least a 6 mmHg separation between intensive BP control and usual BP control arms at month 8. A secondary outcome will be the difference in BP between the two treatment strategies at study closeout. Adherence to home BP monitoring will be measured by the number of weeks participants successfully complete the minimum number of home readings.

Safety of our intervention will also be a secondary outcome and will be determined by a composite of adverse events including hyperkalemia ($K \ge 6.0 \text{ meq/L}$), self-reported falls, syncope, or acute kidney injury (AKI) requiring emergency room visit or hospitalizations. Discharge summaries from emergency room visits and hospitalizations in patient health records will be reviewed and events adjudicated by two study investigators. In addition, onset of ESKD will not be a censoring event; patients will be encouraged to continue to check home BPs following transplant or dialysis, but no study-driven active titration of antihypertensive agents will occur after ESKD onset.

Statistical analysis

Safety outcomes, or rates of adverse events, will be tallied using simple proportions and descriptive statistics. Intention-to-treat analysis will be performed. Stratified analyses by diabetes status will be performed given the lack of robust trial data to support intensive BP lowering in patients with diabetes. We will also test for differences in the composite rates of hospitalizations, emergency room visits, and hyperkalemia in the two arms. We will explore differences in the rates of ESKD or cardiovascular events and determine if there is any effect modification of the intervention by level of proteinuria or by diabetes. For patients lost to follow-up, we plan to use chained multiple imputation to perform analyses.

Sample size rationale

Randomizing 96 participants to strict vs usual BP control will provide 80% power (with 2-sided α of 0.05) to detect a 6-mmHg difference in SBP (with SD difference of 10 mmHg) between the two arms at month 8. Anticipating approximately 25% dropout, we plan to enroll 120 participants. An effect size of similar magnitude has been reported previously in telemonitoring feedback from pharmacists in adult home BP monitoring trials (37).

List of Abbreviations

BP- blood pressure

CKD- chronic kidney disease

CV- cardiovascular

SBP- systolic blood pressure

ESKD- end-stage kidney disease

SPRINT- Systolic Blood Pressure Intervention Trial

eGFR- estimated glomerular filtration rate

MDRD- Modification of Diet in Renal Disease

RAAS- renin-angiotensin-aldosterone system

AKI- acute kidney injury

BMP- basic metabolic panel

UPCR- urine protein creatinine ratio

ABPM- ambulatory blood pressure monitoring

DBP- diastolic blood pressure

MAP- mean arterial pressure

ARB- angiotensin receptor blockers

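### Home-monitoring adherence is measured by a number of completed weeks, although the number of weeks requested differs between participants

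*Protocol*

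**What the plan says.** The Protocol, under Outcomes measures, defines the measure in one sentence: "Adherence to home BP monitoring will be measured by the number of weeks participants successfully complete the minimum number of home readings". The minimum is not repeated there. The section on home blood pressure readings sets it at 6 per week, in the context of titration: "with a minimum of 6 required readings per week to be considered sufficient for any changes to medications". The same section adds: "An insufficient number of measurements will prompt contact with the participant to increase the number of readings".

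The Follow-Up Timeline sets how many weeks are requested:

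- Initial phase: "Participants are instructed to take weekly home BP readings for the first 4 months of the study, or until target SBP levels are achieved". The sentence goes on to require that the target hold for two consecutive weeks.
- After target: "Once participants reach target SBP levels, home BP readings can be taken on a monthly basis over a one-week period each month".
- After month 8: "If participants maintain their target SBP levels after 8 months, home BP readings can be taken every two months thereafter".
- When weekly mean SBP is more than 4 mmHg outside the target range: "antihypertensive therapy titration is resumed weekly until target SBP levels are achieved again for two consecutive weeks".
- Length of follow-up: "Participants will be followed indefinitely unless they choose to disenroll from the study or are lost to follow-up".

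After ESKD onset, Outcomes measures says that home readings are encouraged but study-driven titration stops. Neither the Protocol's Statistical analysis section nor the SAP mentions home-monitoring adherence. The text gives no denominator, counting period or summary statistic for it.

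**The concern.** A count of completed weeks works as an adherence measure when everyone is asked for the same number of weeks. Here they are not. A participant who reaches target quickly moves to monthly readings and is asked for fewer weeks. One who takes most of the four months is asked for more, and so may be one whose titration resumes or who stays in the study longer. The reduced schedules are also worded as permission, so a participant who keeps reading more often than asked adds to the count.

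In a feasibility pilot whose titration runs on home readings, this is the only stated measure of whether participants keep supplying them. From the count alone, a low value may reflect missed weeks, early BP control or short follow-up, and the reader cannot tell which.

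**Working it through.** The documents state no adherence figure, target or expected number of weeks, so there is no figure of the plan's own to reproduce. The check counts the weeks requested under the Follow-Up Timeline.

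**Inputs from the Protocol.** Weekly readings until target has held for two consecutive weeks; then one week per month to month 8; then one week every two months if target is maintained.

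**Assumptions.** One month = 365.25/12/7 = 4.348 weeks, so month 4 = 17.39 weeks and month 8 = 34.79 weeks. The baseline week is excluded. There is no relapse into resumed titration. The least frequent schedule allowed is followed.

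**Formula.** If the weekly phase ends at week w (no later than month 4):

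requested weeks to month 8 = w + (34.79 − w)/4.348

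| Weekly phase ends | Calculation | Requested weeks to month 8 |
|---|---|---|
| Week 2 (earliest possible) | 2 + 32.79/4.348 | 9.54 |
| Week 4 | 4 + 30.79/4.348 | 11.08 |
| Week 12 | 12 + 22.79/4.348 | 17.24 |
| Week 17 (close to month 4) | 17 + 17.79/4.348 | 21.09 |

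**Ties to month 8.** A tie is the adherence at which the later responder has the same count as a fully adherent earlier responder.

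- Week 4 v week 12: 11.08/17.24 = 0.643, about 64%. In whole weeks, 11/17 = 0.647 or 12/18 = 0.667.
- Week 2 v week 17: 9.54/21.09 = 0.452, about 45%. In whole weeks, 9/21 = 0.429, 10/22 = 0.455 or 10/21 = 0.476.

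**To month 12.** Four months at one week per two months adds 4/2 = 2 weeks to each. The ties become 13.08/19.24 = 0.680 and 11.54/23.09 = 0.500.

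**Length of follow-up.** If counting continues beyond month 12, each further year adds 12/2 = 6 weeks for a participant who stays on target and completes every period, with no change in adherence.

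**Effect of a denominator.** In whole periods for the week 4 and week 12 pair, both participants have a count of 11. Completed over requested gives 11/11 = 100% and 11/17 = 65%, which separates them.

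**The case against.** The strongest reply is that little rests on the measure. The month-8 separation is labelled primary, and the closeout BP difference and safety are labelled secondary. The adherence sentence has no such label and no threshold, test or decision rule. It names what is counted, and does not say that bare totals will be reported or compared between participants. An analyst might well set the count against the weeks requested. This stands as to weight. It does not remove the point, because no denominator is written down and the obvious one is not fully determined by the text.

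The magnitudes are chosen scenarios. The documents give no distribution of time to target, and the week 2 and week 17 pair is the extreme one. If weekly readings resume along with titration, a relapse in the early responder narrows the gap. This stands, so the figures are illustrations only.

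The counting window is absent from the text reviewed, which does not show Figure 1. The Protocol describes that figure as a timeline of visits, so it may not settle the matter. The text also does not say that counting runs past the first year.

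A simple ratio needs rules of its own. Missing weeks can leave target status unknown, the monthly week is not fixed, and the schedule for participants off target after month 4 is unclear. This stands, and the fix has to supply those rules.

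A reader might infer three stronger things. One is that the count says nothing about adherence. That goes too far: it can be interpreted once the weeks requested are known. Another is that the arms are distorted because their targets differ. Time to target may differ by arm, but the documents give neither direction nor size and plan no between-arm test of this measure. A third is a much wider spread, from assuming weekly readings right through to month 8. That depends on an unclear clause for participants off target, or on controlled participants volunteering weekly readings, which nothing in the text leads one to expect.

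**Conclusion.** The concern holds as a minor, optional improvement. The plan measures home-monitoring adherence by a number of completed weeks while asking different participants for different numbers of weeks. The count alone therefore combines adherence with BP response and follow-up. On the least frequent schedule and with no relapse, full adherence in an earlier responder can equal about 64% in a later one (week 4 v week 12), or about 45% in the extreme pair (week 2 v week 17), to month 8. How often such pairs would occur cannot be judged from the documents. The primary outcome and the sample size are unaffected, and no bias between arms is shown.

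**What to change.** Replace the count, in both the Protocol and the SAP, with completed over requested periods per participant, from randomization to month 8 and to month 12. The definition needs these rules:

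- **Weekly phase.** Weeks with at least 6 readings, divided by weeks elapsed. A week with missing or insufficient readings counts as requested and not completed. For counting, the phase ends only when two consecutive sufficient weeks at target are recorded.
- **Monthly or two-monthly phase.** Months (or two-month periods) containing at least one week with 6 or more readings, divided by periods elapsed. The choice of week and any voluntary extra weeks then make no difference.
- **Off target after month 4, or in resumed titration.** State which reading schedule is counted. The initial-phase sentence can be read as ending weekly readings at month 4 or as continuing them until target, and the resumption sentence refers to titration and not to readings. The sponsor must clarify the Follow-Up Timeline on this; the review takes no position on which schedule is right.
- **After ESKD onset.** Report these weeks separately, because readings are then only encouraged.

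The cost is some extra derivation and these few counting rules. Readings are already held on the device platform described under Home blood pressure monitor, and trial conduct does not change.

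### The safety composite captures only AKI that reaches emergency or hospital care; the >30% creatinine rise the protocol acts on is not a named safety outcome, and AKI has no laboratory definition

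*Protocol*

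**What the plan says.** Protocol, Outcomes measures: safety is a secondary outcome, judged by a "composite of adverse events including hyperkalemia" at or above 6.0 meq/L, falls reported by the participant, syncope, or "acute kidney injury (AKI) requiring emergency room visit or hospitalizations". The ascertainment text that follows is: "Discharge summaries from emergency room visits and hospitalizations in patient health records will be reviewed and events adjudicated by two study investigators". No laboratory source is named for adjudication, and neither document gives a creatinine criterion for AKI.

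Protocol, Antihypertensive Therapy Titration Intervention: "For patients who experience >30% increase in serum creatinine, the ACEi/ARB dose or other antihypertensive medication will be reduced". A repeat value follows within 2 weeks, and the ACEi/ARB is stopped if the elevation persists. The same section says participants are "contacted every other week by study coordinators to note any adverse events including dizziness, falls, syncope, hospitalizations, emergency room visits, acute kidney injury", among other events, during the first 8 months. AKI carries no emergency or hospital condition there.

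Protocol, Laboratory Tests: metabolic panels are "obtained at baseline and at months 1, 2, 4, 8, 12, and every six months thereafter", with extra tests as needed.

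Protocol, Statistical analysis, and SAP, Statistical Analysis: "Safety outcomes, or rates of adverse events, will be tallied using simple proportions and descriptive statistics". The one safety composite to be formally tested consists of hyperkalemia, hospital admissions and emergency visits. ESKD is compared on an exploratory basis.

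**The concern.** The protocol has two ways of looking at the kidney, and they do not meet. One is a management rule that responds to a creatinine rise, usually before anyone needs acute care. The other is a safety outcome that starts counting only when acute care is reached. A rise found at a study panel, handled by a dose change and settled without a hospital contact enters neither the safety composite nor the tested composite.

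The trial is a pilot whose stated purpose includes safety, in patients with eGFR at or below 30. If stricter control produces more rises beyond the protocol's own limit, that is information the pilot should deliver. As written, the arms could look alike on the AKI component while differing on the laboratory measure. The trial is also unblinded, and nephrology providers are told the assigned target. Referral to acute care can be influenced by knowledge of the arm, whereas creatinine on a schedule common to both arms is less open to that influence.

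**Working it through.** The plan states no AKI rate, creatinine-event rate or safety power, so there is no figure to reproduce. The check is mainly textual.

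**Step 1. Where could an outpatient >30% rise be counted?**

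| Place in the plan | Would it count? |
|---|---|
| Safety composite (Protocol, Outcomes measures) | Not under the AKI component, which needs an emergency visit or admission |
| Adjudication (same section) | Not from the named source, which is discharge summaries |
| Tested composite (Protocol and SAP, statistical sections) | No; neither AKI nor creatinine is named |
| Contacts every two weeks (Protocol, titration section) | Possibly, as AKI; the term is undefined, the source is participant contact, and the schedule stops at 8 months |
| General adverse-event tally (Protocol and SAP) | Possibly; not stated |
| ESKD comparison (exploratory) | Only if the participant reaches dialysis or transplant |

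The rise is therefore not expressly excluded from safety recording, but no named outcome captures it. Dose reductions and ACEi/ARB stops that follow from it are likewise in no outcome.

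**Step 2. Could the data supply it?** Panels fall "at baseline and at months 1, 2, 4, 8, 12, and every six months thereafter", on the same schedule in both arms, so the laboratory values exist. For dose changes, the Protocol says only that titrations by non-study providers are noted (Blood Pressure Targets). Recording of study-driven changes is not described.

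**Step 3. Illustration with assumed rates.** Only the allocation comes from the documents: 2:1 for the first 75 gives 50 and 25; 1:1 for the remaining 45 gives 22.5 each. The expected arms are 50 + 22.5 = 72.5 (intervention) and 25 + 22.5 = 47.5 (usual care).

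Assume a >30% rise in 15% versus 5%, with a share *s* of rises reaching emergency or hospital care in both arms.

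- All rises: 0.15 × 72.5 = 10.9 and 0.05 × 47.5 = 2.4; difference 15 − 5 = 10 points.
- Counted at *s* = 20%: 10.9 × 0.2 = 2.2 and 2.4 × 0.2 = 0.5; difference 10 × 0.2 = 2 points.
- At *s* = 10% the difference is 10 × 0.1 = 1 point; at *s* = 50% it is 10 × 0.5 = 5 points.

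A second set of assumptions uses higher rates, arms rounded to 72 and 48, and *s* from 25% to 75%. Power is for comparing two proportions.

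| Assumed rise, intervention vs usual care | All rises | Counted | True difference (points) | Recorded difference (points) | Power, all rises | Power, counted |
|---|---|---|---|---|---|---|
| 20% vs 10% | 14.4 vs 4.8 | 3.6–10.8 vs 1.2–3.6 | 10 | 2.5–7.5 | 30% | 9–22% |
| 40% vs 20% | 28.8 vs 9.6 | 7.2–21.6 vs 2.4–7.2 | 20 | 5–15 | 64% | 15–47% |

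With a common share, the recorded difference is simply the true difference times *s*. If the share differs by arm, even the direction is not safe: with 15% versus 5%, and 10% of intervention rises but 50% of usual-care rises reaching acute care, the recorded difference is 15 × 0.1 − 5 × 0.5 = −1 point.

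**The case against.** The strongest reply is that the plan does not confine safety recording to hospital events. AKI is on the list for the two-weekly contacts without any hospital condition, adverse events are ascertained during follow-up, and their rates are tallied. The composite is introduced with a word that may leave its list open. All of this stands. A reader might infer that a >30% rise is never counted; the documents do not say so. They are silent on whether such a rise is entered as AKI or as an adverse event. What remains is that this route is weak and that nothing ties it to the laboratory values.

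A >30% rise is also not shown to be AKI or harm. The protocol treats it as a trigger for action and a repeat test, and some rises will reverse or reflect progression of CKD. That stands too: the point concerns an unreported safety signal, not proven injury.

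Two further inferences are tempting and unsupported. One is that potassium is treated more strictly than creatinine because hyperkalemia counts wherever it is found. That depends on whether the emergency/hospital condition attaches to AKI alone or to the whole list, and the sentence can be read either way. The other is that creatinine events decide feasibility. The Protocol defines feasibility by a blood pressure separation of at least 6 mmHg at month 8; creatinine-driven dose changes may affect that separation but do not define it.

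Finally, every event rate in the illustration is assumed. It shows how dilution works, not how large it will be.

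**Conclusion.** The point holds in this form: the composite captures only AKI that reaches emergency or hospital care, the >30% rise that the protocol acts on is not a named safety outcome, and AKI has no laboratory definition. Kidney events managed in the outpatient setting can drop out of the composite, and the between-arm safety comparison may then be falsely reassuring. The exploratory ESKD comparison does not fill the gap, because it registers only dialysis or transplant.

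The size cannot be derived from the documents. Under the assumed rates above, a 10-point difference shrinks to 1 to 5 points in the first set, and differences of 10 to 20 points shrink to 2.5 to 15 points in the second. Both results rest on the assumed rates and on an equal share reaching acute care in each arm. The primary outcome is unaffected. This is a worthwhile, inexpensive improvement to safety reporting, not a flaw that invalidates the trial.

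**What to change.** In the SAP:

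1. Keep the emergency/hospital AKI component, report it separately, and state the definition of AKI used.
2. Add a safety outcome by arm: the proportion with a creatinine rise above 30% from the pre-randomization value at the scheduled labs of months 1, 2, 4 and 8, and also through month 12. Use scheduled labs only for the comparison, since as-needed testing may differ by arm. Set visit windows, because panels are timed around clinical tests.
3. Count values up to ESKD onset and show ESKD alongside. ESKD does not censor follow-up in this trial, and creatinine after dialysis or transplant is not comparable.
4. Show how many rises persisted on the repeat test. The rise in item 2 is cumulative from randomization, whereas the titration rule concerns rises after a drug is started or increased; the table should say so.
5. Report creatinine-triggered dose reductions and ACEi/ARB discontinuations by arm, descriptively only. They are partly discretionary, since a nephrologist's concern about any rise is enough, and the trial is unblinded. Confirm first that study-driven changes are recorded.
6. State whether laboratory-detected rises are entered as adverse events, and reconcile the safety composite with the differently composed one that is to be tested.

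The cost is SAP wording and one table, using a threshold and panels the Protocol already has. The downside is small: some counted rises will be reversible or reflect CKD progression, so the event rate will look less favorable. No change to the clinical creatinine rule is proposed.
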